6.3.2 Summary Statistics

In general, data will be summarized by means of summary statistics. Continuous data will be presented with the number of observations, mean value, standard deviation, minimum, Q1, median, Q3 and maximum value. Categorical data will be presented as counts and percentages. All efficacy related variables will be summarized for the FAS population and all safety related data will be summarized for the safety population.

For any assessments being evaluated by visit, an LOCF (Last observation carry forward) approach will be applied, where the last available information will be combined, independently of what the last recorded visit is.

All descriptive statistics will be presented by stratum of high- and intermediate risk patients and pooled together and by treatment group.

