6.3.6 Secondary Efficacy Analyses

PFS from start of sunitinib according to RECIST 1.1

PFS from start of sunitinib treatment will be derived as date whichever occurred first of any cause of death or date for first tumor progression (which is date for centrally assessed CT performed, according to RECIST 1.1) minus date for start of sunitinib treatment plus 1 day.

For the analysis of PFS only deaths occurring before end-of-trial will be accounted for in the analysis.

Analysis of PFS will be evaluated the following way:

Survival functions will be displayed graphically using Kaplan-Meier plots, and life table statistics will be produced including summaries of number of events and censored observations. Estimates of cumulative 25%, 50% (median) and 75% percentiles of survival with corresponding 95% confidence intervals will be calculated.

Comparison between Intuvax+sunitinib, vs. sunitinib alone will be done using a stratified log-rank test (controlling for strata intermediate/high risk), separate analyses will also be done by strata.

With protocol versions before version 4.0, intermediate risk patients did not have to initiate treatment with sunitinib at a fixed time point according to the visit schedule. Consequently some patients were never started on sunitinib, and in some cases sunitinib treatment was initiated at a later time point. The sunitinib start date constitutes the baseline time point for PFS according to protocol version 4.0 and after. In the analyses, patients who either had a delay or never started sunitinib will be included under the assumption that sunitinib treatment would have been initiated according to the final design, the date of the visit following the nephrectomy visit will be used as baseline.

Another issue that will be considered in the analysis is that some patients may have been discontinued based on general clinical disease progression as evaluated by investigator from symptoms/signs of disease, rather than based on a PD according to RECIST 1.1. For the analysis such cases will be handled strictly based on the RECIST 1.1 evaluation, thus if a patient is withdrawn without a CT confirmed PD the subject will be censored at last CT

Analyses will be based on FAS and repeated for separately by strata..

Proportion of Objective Response Rate (ORR) and Disease Control Rate (DCR) from start of sunitinib

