Proportion of ORR from start of sunitinib treatment will be derived as the proportion of patients with the individual's best overall response scored as "CR" or "PR" (using RECIST 1.1) across all time points from first visit six (6) weeks after sunitinib treatment, to end-of-study visit. Similarly, DCR will be derived as proportion of patients with best overall response scored as "CR", "PR" or "SD".

ORR and DCR will be summarised and comparison of treatment groups will be made using the Cochran Mantel-Haenzel test, adjusting for strata.

Duration of response will be derived only for patients meeting the ORR definition CR or PR, at least once, as the date of the first occurrence of PD or death minus the date at which the CR or PR was first observed, plus 1 day. Patients without an occurrence of a PD or death after CR or PR will contribute with the time up till last tumor assessment. Data will be summarised descriptively.

Duration of clinical benefit will be derived only for patients meeting the DCR definition CR, PR or SD at least once, as the date of the first occurrence of PD or death minus the date at which the CR, PR or SD was first observed, plus 1 day. Patients without an occurrence of a PD or death after CR, PR or SD will contribute with the time up till last tumor assessment. Data will be summarised descriptively.

The duration of stable disease is calculated for only those patients who exhibited a best response of stable disease response and will be calculated as the date for the first SD

response to the date of the first observed progression of disease or death before end of trial, if the death was due to disease progression (whichever comes first) plus 1 day. Data will be summarised descriptively.

Response rate from Sunitinib Start Visit

Evaluation of response rate, based on CT and according to the RECIST 1.1 guideline, from Sunitinib Start Visit will be based on the subpopulation from FAS who have been exposed to at least one dose of sunitinib. Number of patients with CR, PR, PD, and SD after start of sunitinib will be summarized using the underlying ordinal scale.

Waterfall charts will be used to display the percent change in target lesion tumour dimension vs best overall response and Two types of Swimmer plots will be created, one with bars showing time from randomization and one from sunitinib start. In these events for progressive disease, end of trial and vital status will be indicated.

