6.6 Handling of Dropouts and Missing Data

Primary and secondary efficacy endpoint

The primary and secondary efficacy endpoint analysis will be conducted on available data (observed cases). Missing data due to loss of follow-up and rules for censoring will be done as described in each corresponding section.

Handling of incomplete dates

Incomplete (partial or missing) dates will be presented in data listings as provided on the eCRF. However, for use in calculations (e.g. to calculate the duration of an AE or medication use) dates will be estimated as follows.

For partial start-dates

- If the year is unknown, then the date will not be imputed and will be assigned a missing value
- If the month is unknown, then:
 - If the year matches the year of the first dose date, then impute the month and day of the first dose date
 - Otherwise, assign 'January'
- If the day is unknown, then:
 - If the month and year match the month and year of the first dose date, then impute the day of the first dose date.
 - Otherwise, assign 'January'.

For partial end-dates,

- If the year is unknown, then the date will not be imputed and will be assigned a missing value.
- If the month is unknown, then assign 'December'.
- If the day is unknown, then assign the last day of the month

If the above rules for end-dates result in a date after the patient was ended the study, then the end date will be replaced with the patient's date of completion/withdrawal. Furthermore, should the above rules not result in the most conservative date (as described below), then the imputed value may be replaced by a date that will lead to a more conservative analysis.

After implementing the rules above, to determine whether AEs with incomplete start or stop dates are pre-treatment or treatment-emergent the following strategy will be used:

- If the start date and stop date are both missing, the most conservative approach is taken and the AE is considered to be treatment-emergent
- If the start date is missing but the stop date is not missing and is on or after the day of first study drug administration but before or on the Week 12 visit date then the most conservative approach is taken and the AE is considered to be treatment-emergent;
- If the start date is missing but the stop date is not missing and is before the day of first study drug administration then the AE is considered to be pre-treatment.

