14.2 EFFICACY DATA

(Efficacy presentations will be split by stratum, all presentation will be based on FAS if not otherwise stated below)

Tables

- 14.2.1 Life table statistics of OS by treatment group (FAS, PPS and Subgroups)
- 14.2.2 Quartile Estimates (Median) and Confidence Intervals for OS (FAS, PPS and Subgroups)
- 14.2.3 Log rank test compare survival functions for treatments groups OS (FAS, PPS and Subgroups)
- 14.2.4 The estimates of the second primary endpoint of the proportion of 18-months survival and corresponding z-test test. (FAS, PPS and Subgroup)

- 14.2.7 Life table statistics of PFS from start of Sunitinib by treatment group
- 14.2.8 Quartile Estimates (Median) and Confidence Intervals for PFS from start of Sunitinib (FAS and Subgroup)
- 14.2.9 Log-Rank test compare survival functions for treatment groups PFS from start of Sunitinib (FAS and Subgroup)
- 14.2.13 Summary of RECIST 1.1, Number of patients with CR, PR, PD, SD, and "Not Evaluable" by visit from Screening to Sunitinib Start Visit (FAS and Subgroup)
- 14.2.14 Summary of RECIST 1.1, Number of patients with CR, PR, PD, SD, and "Not Evaluable" by visit after Sunitinib Start Visit (FAS and Subgroup)
- 14.2.15 Summary of ORR and DCR from start of Sunitinib (FAS and Subgroup)
- 14.2.16 Cochran Mante -Haenze test for ORR and DCR (FAS and Subgroup)
- 14.2.17 Summary of duration of response, and duration of clinical benefit (FAS and Subgroup)
- 14.2.18 Summary of duration of stable disease (FAS and Subgroup)
- 14.2.19 Life table statistics of TTP from start of Sunitinib by treatment group (FAS and Subgroup)
- 14.2.20 Quartile Estimates (Median) and Confidence Intervals for TTP from start of Sunitinib (FAS and Subgroups)
- 14.2.21 Log-Rank test compare survival functions for treatment groups TTP from start of Sunitinib (FAS and Subgroups)
- 14.2.22 Summary of tumor infiltrating CD8+ T-cells and relative number of tumor infiltrating CD8+ T-cells, [REDACTED] and [REDACTED] (FAS and Subgroups)
- 14.2.23 Summary of ECOG performance by visit (FAS and Subgroups)
- 14.2.24 [REDACTED]
- 14.2.25 Summary of immunohistology parameters (CD8+ T-cells) in a biopsy from adjacent normal kidney tissue collected approximately 2 cm from the tumor margin and in a metastasis biopsy where applicable, [REDACTED] and [REDACTED] (FAS and Subgroups)

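### Durations of response, clinical benefit and stable disease are planned as plain summaries without censoring, and the SAP's death rules for response duration and TTP differ from the protocol's

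*SAP*

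**What the plan says.** **Durations in the SAP.** SAP 6.3.6 measures duration of response from first CR or PR to first PD or death, with no condition on the cause or date of death. For responses still ongoing: "Patients without an occurrence of a PD or death after CR or PR will contribute with the time up till last tumor assessment". Clinical benefit (CR, PR or SD) has the same wording. Duration of stable disease ends at PD or at a death due to progression before end of trial; nothing is said about patients still stable. All three are to be summarised descriptively. SAP 6.3.2 states what that means: "Continuous data will be presented with the number of observations, mean value, standard deviation, minimum, Q1, median, Q3 and maximum value".

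**Censoring in the SAP.** SAP 6.6 defers to the endpoint sections: "Missing data due to loss of follow-up and rules for censoring will be done as described in each corresponding section". The PFS text gives such a rule ("thus if a patient is withdrawn without a CT confirmed PD the subject will be censored at last CT") and restricts deaths: "For the analysis of PFS only deaths occurring before end-of-trial will be accounted for in the analysis". The TTP text censors at the last CT any patient who dies without earlier radiological or clinical progression.

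**Protocol.** Section 10.1 lists duration of response as a secondary endpoint. Section 10.2.2.2 ends a response at progression or at a death due to progression, and 10.2.2.3 counts a death due to progression as a TTP event. Section 12.1.6 applies the PFS survival approach to the other time-to-event secondary endpoints.

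**The concern.** A response still ongoing at the last scan has a known minimum length and an unknown true length. Entering that minimum in a mean or quartile as if it were complete biases the mean downward. It also biases the raw median when responses are long relative to follow-up or when scanning stops early. The arm with longer responses has more ongoing ones and loses more, so a real difference shrinks. Protocol 5.2 postulates a more durable response with the vaccine, which is the feature this summary blunts.

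The end events are a second problem. SAP 6.3.6 applies three death rules: any death for response and clinical benefit, progression death for stable disease, and no death for TTP. Two of these contradict the protocol's definitions. For response and clinical benefit it is also open whether a death found in post-study survival collection ends the duration.

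**Working it through.** The plan gives no expected duration, response rate or event count, so there is no stated figure to reproduce.

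**1. What the text instructs**

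| Endpoint | Patient without event | Deaths that count (SAP) | Deaths that count (protocol) | Planned tables |
|---|---|---|---|---|
| PFS | censored at last CT if withdrawn without CT-confirmed PD | any, before end of trial | any after sunitinib start | life table, quartiles with CI, log-rank (14.2.7-14.2.9) |
| TTP | as PFS | none; censored at last CT | due to progression | life table, quartiles with CI, log-rank (14.2.19-14.2.21) |
| Response | contributes time to last assessment | any, no date limit | due to progression | summary (14.2.17) |
| Clinical benefit | contributes time to last assessment | any, no date limit | due to progression, if the combined duration in 10.2.2.2 inherits that rule | summary (14.2.17) |
| Stable disease | no rule | due to progression, before end of trial | due to progression | summary (14.2.18) |

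No Kaplan-Meier plot is listed for any duration. As written, a programmer has no censoring indicator to set and no estimator that would use one.

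**2. Observable window** (visit windows in Protocol 7.2.1 and Table 2)

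End of study is week 78, day 546.

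- Vaccine arm: sunitinib starts between day 19 + 35 = 54 and day 63 + 56 = 119. That leaves (546 - 119)/7 = 61.0 to (546 - 54)/7 = 70.3 weeks. Less 6 weeks to the first scan, the longest observable response is 55.0 to 64.3 weeks.
- Control arm: no earliest nephrectomy day is set. Sunitinib start at day 1 + 35 = 36 gives (546 - 36)/7 - 6 = 66.9 weeks.
- The +2-week visit window raises the maxima to about 66 and 69 weeks.

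**3. Hand check of the mean**

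For an exponential duration with median m, the true mean is μ = m/ln 2. If follow-up stops at C, the share ongoing is 2^(-C/m) and the raw mean is μ(1 - 2^(-C/m)). Take C = 55 weeks = 385/30.44 = 12.65 months:

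- m = 6: μ = 8.66, ongoing 0.232, raw mean 8.66 × 0.768 = 6.65 months.
- m = 12: μ = 17.31, ongoing 0.482, raw mean 17.31 × 0.518 = 8.97 months.

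The raw mean ratio is 8.97/6.65 = 1.35, against a true 2.0.

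**4. Simulation**

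Assumptions, none from the documents: exponential durations; first response at week 6, 12 or 24 with probability 0.5, 0.3 and 0.2; sunitinib start uniform over days 54-119 (vaccine) and 36-119 (control); early loss of scans 0 or 3% per month; 200,000 patients per arm. Figures are control vs vaccine, in months; a slash separates no early loss from 3% loss.

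| True medians | Raw medians (ratio) | Raw mean ratio | Kaplan-Meier medians |
|---|---|---|---|
| 4 vs 8 | ratio 1.99 / 1.74 | 1.48 / 1.44 | 4.0 vs 8.0 |
| 6 vs 12 | 6.0 vs 9.8 (1.64) / 4.8 vs 7.8 (1.64) | 1.30-1.34 | 6.0 vs 12.0 |
| 8 vs 16 | 8.0 vs 11.0 (1.37) / 5.9 vs 8.9 (1.50) | 1.23-1.25 | 8.0 vs not reached |
| 6 vs 6 and 12 vs 12 | ratio 0.98-1.01 | 0.98-0.99 | equal |

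At 6 vs 12, 23-33% of control and 49-56% of vaccine responses are ongoing at the last scan. With progression seen only at scheduled scans, the raw ratios fall to 1.47-1.50 (median) and 1.22-1.24 (mean), against 6.9 vs 12.5 by Kaplan-Meier. At a realistic size of 12 vs 24 responders (40% of 30 and 60), the typical ratio is 1.59-1.62 on raw medians and 1.31-1.34 on means. There the Kaplan-Meier median is not reached in 1-3% of control and 29-34% of vaccine samples.

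**5. Open limit on deaths**

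Sunitinib starts on day 54, response is seen 6 weeks later on day 96, and the patient is still responding on day 546. If alive, the duration is 546 - 96 + 1 = 451 days. If a death 365 days later (day 911) counts, it is 911 - 96 + 1 = 816 days.

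**6. TTP**

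Suppose a share p of progressions appears only as a progression death and is censored at the previous scheduled CT. A true median of 8.0 months then reads about 8.4, 8.8 or 9.8 for p = 5%, 10% or 20% (roughly 8/(1 - p)). With no true difference, the hazard ratio (vaccine vs control) is 0.99 at equal 10% shares, 1.10 at 5% vs 15%, and 0.89 at 15% vs 5%.

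**The case against.** - **Censoring may be implied.** Stating that an ongoing case contributes time to its last assessment says where the clock stops, which is half of a censoring rule. But no censored status is assigned, and the only summary planned cannot use one. The SAP uses the word censored for OS, PFS, TTP and TTF, where it means it.
- **Protocol 12.1.6 may not reach these endpoints.** It opens by calling secondary endpoints descriptive, and its time-to-event sentence most plainly covers TTP. Clinical benefit and stable disease durations are not listed in Protocol 10.1. That stands for those two. Duration of response is listed and is defined as time to an event.
- **The sizes rest on assumptions.** They do. At 4 vs 8 months without early loss, raw medians are correct. The simulated arm gap in sunitinib start averages only 9 days, while Protocol 9.1.1 states a 14 to 20 day delay of nephrectomy in the vaccine arm. A 17-day shift moves the no-difference mean ratios to about 0.97-0.98. With a vaccine window 2.5 weeks shorter and other response timings, equal true medians of 12 months read 9.1 (control) and 8.5. Any spurious effect is small and goes against the vaccine.
- **Kaplan-Meier does not cure everything.** Patients leave at locally verified PD while endpoints use central reads, so some censoring is probably informative. This stands as a caution, but the raw summary has the same weakness as well.
- **TTP.** The SAP counts clinical progression, so only progression deaths with no earlier sign are lost. Avoiding attribution of deaths in an open-label trial is defensible, but it is a change from the protocol's definition and needs stating.
- **Non-declaration.** Two bullets in SAP 6.1 are blacked out, so only the visible text can be said to be silent.
- **Low stakes.** The analyses are exploratory, no test between arms is planned for durations, and swimmer plots show progression, end of trial and vital status. This limits the severity, but the plots do not correct the tabulated means and medians.

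**Conclusion.** The concern holds. Followed as written, the SAP tabulates incomplete durations as complete ones, and it has no rule for patients still in stable disease. Its end events for response duration and TTP contradict Protocol 10.2.2.2 and 10.2.2.3, and the date limit on deaths is missing for response and clinical benefit. Those textual findings need no assumptions.

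The size does. Under exponential durations and the assumed response times, a true doubling of the median shows as 1.37 to 1.99 on raw medians and 1.23 to 1.48 on means. The TTP effect is probably modest unless progression deaths without earlier progression are common or unequal between arms. The primary endpoints are untouched. This should be fixed before database lock, but it does not threaten the trial's main analysis.

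**What to change.** 1. Analyse duration of response, clinical benefit and stable disease by Kaplan-Meier, by arm. Censor patients without an event, including those still in SD, at their last tumor assessment. Report the number ongoing and the median with 95% CI, or state that it was not reached.
2. Use one end event for all three, consistent with Protocol 10.2.2.2 (death due to progression), or declare and justify the change to any death in SAP 6.1. State the same end-of-trial limit on deaths for all three.
3. Count on-study deaths due to progression as TTP events, as in Protocol 10.2.2.3, or declare and justify the change in SAP 6.1.
4. Replace the shells of Tables 14.2.17 and 14.2.18.

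The cost is SAP wording, two shells and code. The dates of response, PD, last scan and death are already needed for planned outputs. Cause of on-study death is also needed, and the SAP's stable-disease rule already relies on it. Because Protocol 11.2 tells sites not to report progression itself as an adverse event term, attribution may need a short documented review of on-study deaths before database lock. It cannot extend to post-study deaths, for which the protocol plans to collect only the date.

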10.2.2 Secondary Efficacy Variables and Assessments

10.2.2.1 Progression Free Survival (PFS) from Start of Sunitinib

PFS from start of sunitinib is defined as time from Sunitinib Start Visit to PD or death following sunitinib initiation from any cause, whichever occurred first. PFS from start of sunitinib will be evaluated per stratum and in total from the two (2) different treatment arms as a secondary efficacy variable.

Note: For intermediate-risk patients included in the trial according to protocol versions before version Final 4.0, sunitinib treatment did not have to be initiated at a fixed time point. For these patients, the first imaging assessment after nephrectomy will be used as baseline for evaluation of PFS, irrespective of whether or not the imaging assessment coincided with sunitinib treatment start. Further details will be provided in the Statistical Analysis Plan (SAP).

10.2.2.2 Objective Response Rate and Duration of Response and Stable Disease from Start of Sunitinib

Evaluation of tumor response is based on centrally assessed CT scans, *Section 10.4.3*, according to the RECIST 1.1 guideline [1].

Definitions - RECIST v1.1

a) Measurable Disease

The presence of at least one (1) measurable lesion. If the measurable disease is restricted to a solitary lesion, its neoplastic nature should be confirmed by cytology/histology. The same measurable and non-measurable lesions will be followed by RECIST v1.1. Disease progression will be determined using RECIST v1.1 criteria.

- Malignant lymph nodes

To be considered pathologically enlarged and measurable, a lymph node must be >15 mm in short axis when assessed by CT scan (CT scan slice thickness

recommended to be no greater than 5 mm). At baseline and in follow-up, only the short axis will be measured and followed.

- **Baseline documentation of “Target” and “Non-Target” lesions**
All measurable lesions up to a maximum of 2 lesions per organ and 5 lesions in total, representative of all involved organs, should be identified as target lesions and recorded and measured at baseline.

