 - **Target lesions.** Target lesions should be selected on the basis of their size (lesions with the longest diameter), be representative of all involved organs, but in addition should be those that lend themselves to reproducible repeated measurements. It may be the case that, on occasion, the largest lesion does not lend itself to reproducible measurement in which circumstance the next largest lesion which can be measured reproducibly should be selected. A sum of the diameters (longest for non-nodal lesions, short axis for nodal lesions) for all target lesions will be calculated and reported as the baseline sum diameters. If lymph nodes are to be included in the sum, then only the short axis is added into the sum. The baseline sum diameters will be used as reference to further characterize any objective tumor regression in the measurable dimension of the disease.
 - **Non-target lesions.** All other lesions (or sites of disease) including any measurable lesions over and above the 5 target lesions should be identified as **non-target lesions** and should also be recorded at baseline. Measurements of these lesions are not required, but the presence, absence, or in rare cases unequivocal progression of each should be noted throughout follow-up.

b) Response Criteria

Table 4 Target Lesions Evaluation Criteria

Complete Response (CR)	Disappearance of all target lesions. Any pathological lymph nodes (whether target or non-target) must have reduction in short axis to <10 mm.
Partial Response (PR)	At least a 30% decrease in the sum of the diameters of target lesions, taking as reference the baseline sum diameters
Progressive Disease (PD)	At least a 20% increase in the sum of the diameters of target lesions, taking as reference the smallest sum on study (this includes the baseline sum if that is the smallest on study). In addition to the relative increase of 20%, the sum must also demonstrate an absolute increase of at least 5 mm. (NB : the appearance of one or more new lesions is also considered progression).
Stable Disease (SD)	Neither sufficient shrinkage to qualify for PR nor sufficient increase to qualify for PD, taking as reference the smallest sum diameters while on study

Table 5 Non-Target Lesions Evaluation Criteria

Complete Response (CR)	Disappearance of all non-target lesions and normalization of tumor marker level
Progressive Disease (PD)	Appearance of one or more new lesions and/or unequivocal progression of existing non-target lesions ^a

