
Also called Clinical Benefit Rate is defined as the proportion of subjects with CR or PR or Stable Disease (SD).

e) The duration of response and stable disease

The duration of response is calculated for only those patients who responded. It was the time from first objective response to first observed progression of disease or death if the death was due to disease progression (whichever comes first).

The duration of stable disease is calculated for only those patients who exhibited a best response of stable disease response as per RECIST v1.1. It is the time from first SD response to first observed progression of disease or death if the death was due to disease progression (whichever comes first).

The duration of response and stable disease will also be calculated for the patients who responded and/or had a best response of SD.

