2 STUDY OBJECTIVES

The primary objectives are:

- To evaluate median overall Survival (OS) from randomization in metastatic renal cell carcinoma (mRCC) patients overall and by subgroup, i.e. in high-risk and in intermediate-risk patients separately, receiving two (2) vaccine doses of Intuvax pre-nephrectomy, followed by sunitinib initiated five (5) to eight (8) weeks post-nephrectomy and in non-vaccinated mRCC patients receiving sunitinib initiated five (5) to eight (8) weeks post nephrectomy
- To evaluate 18-month survival rate from randomization in mRCC patients overall and by subgroup, i.e. in high-risk and in intermediate-risk patients separately, receiving two (2) vaccine doses of Intuvax pre-nephrectomy followed by sunitinib post-nephrectomy and in non-vaccinated patients receiving sunitinib post-nephrectomy

The secondary objectives are:

- To evaluate safety and tolerability in high- and intermediate-risk mRCC patients receiving two (2) vaccine doses of Intuvax pre-nephrectomy followed by sunitinib post-nephrectomy and in non-vaccinated patients receiving sunitinib post nephrectomy
- To evaluate progression free survival (PFS) according to Response Evaluation Criteria In Solid Tumors (RECIST) 1.1 criteria from Sunitinib Start Visit in intermediate- and high-risk mRCC patients after receiving two (2) vaccine doses of Intuvax pre-nephrectomy followed by sunitinib post-nephrectomy and in non-vaccinated patients receiving sunitinib post nephrectomy
- To evaluate response and its duration according to RECIST 1.1 criteria from Sunitinib Start Visit in intermediate- and high-risk mRCC patients receiving two (2) vaccine doses of Intuvax pre nephrectomy followed by sunitinib post-nephrectomy and in non-vaccinated patients receiving sunitinib post-nephrectomy
- To evaluate time to tumor progression (TTP) from Sunitinib Start Visit in intermediate- and high-risk mRCC patients receiving two (2) vaccine doses of Intuvax pre-nephrectomy followed by sunitinib post-nephrectomy and in non-vaccinated patients receiving sunitinib post-nephrectomy
- To evaluate the number of infiltrating CD8+ T-cells in available diagnostic pre-biopsy (sample from either primary tumor or metastasis acceptable) and in the resected primary renal tumor in intermediate- and high-risk mRCC patients receiving two (2) vaccine doses of Intuvax pre-nephrectomy and in non-vaccinated patients

- [REDACTED]
- [REDACTED]
- [REDACTED]
- [REDACTED]
- [REDACTED]
- [REDACTED]
- [REDACTED]

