6.3 Hypotheses and Statistical Methods

6.3.1 Definitions

Baseline The date of randomization is defined as baseline for OS and 18-month survival rate.

The centrally assessed CT performed at the Sunitinib Start Visit is defined as CT baseline for evaluation of PFS, response rate and TTP after start of sunitinib in intermediate- and high-risk patients

The Screening Visit is defined as baseline for all other assessments than those listed above.

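### Duration of stable disease and duration of clinical benefit start at the first qualifying scan, not at the sunitinib baseline, so they run at least 5 to 7 weeks short and depend on which scans were done

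*SAP*

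**What the plan says.** SAP section 6.3.6, under ORR and DCR, defines three durations.

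- **Duration of response** runs from the first CR or PR.
- **Duration of clinical benefit** is for patients with CR, PR or SD at least once. It is the date of progression or death "minus the date at which the CR, PR or SD was first observed, plus 1 day". Patients with neither event are counted to their last tumor assessment.
- **Duration of stable disease** is for patients whose best response is SD. It "will be calculated as the date for the first SD" response up to progression, or death if due to progression.

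Protocol section 10.2.2.2 e) gives the same start for stable disease: "It is the time from first SD response to first observed progression of disease". The heading of that section is "Objective Response Rate and Duration of Response and Stable Disease from Start of Sunitinib".

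Protocol Table 4 defines SD as "Neither sufficient shrinkage to qualify for PR nor sufficient increase to qualify for PD, taking as reference the smallest sum diameters while on study". SAP section 6.3.1 fixes the starting scan: "The centrally assessed CT performed at the Sunitinib Start Visit is defined as CT baseline for evaluation of PFS, response rate and TTP". PFS in SAP section 6.3.6 counts from the start of sunitinib. The SD and clinical-benefit durations are summarised descriptively, in SAP tables 14.2.17 (with duration of response) and 14.2.18.

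**The concern.** A response is a change that is first documented at a particular scan, so that scan is a sensible start for its duration. SD is the absence of sufficient change since a reference scan. At the first post-baseline scan the only earlier reference is the Sun-Start CT, so SD at week 6 is a statement about the interval from Sun-Start to week 6. A clock that starts at week 6 discards that interval.

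The start also moves with attendance. If the week-6 scan is missed or cannot be evaluated, the clock starts at week 12 although the course of disease is the same. At stake is whether table 14.2.18 and the clinical-benefit part of table 14.2.17 can be read as how long disease was controlled on sunitinib, and compared between patients.

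**Working it through.** The documents state no figure for these durations, so there is none to reproduce. The check is date arithmetic on the scan schedule.

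**Inputs**
- Scans at 6, 12, 24, 36, 48 and 60 weeks after Sun-Start, each ±7 days (Protocol section 7.2.1.6 and Table 2).
- First time point that counts for best response: the 6-week visit (SAP section 6.3.6).
- SD reference: for progression, Table 4 takes the smallest sum, and "this includes the baseline sum if that is the smallest on study"; for partial response it takes the baseline sum. At the first scan both comparisons go back to Sun-Start.

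**Formulas** (day 0 = Sun-Start, taken as the day sunitinib starts)
- Plan: end date − first qualifying scan + 1.
- From Sun-Start: end date − 0 + 1.
- Shortfall: day of the first qualifying scan.

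**Shortfall by first scan scored**
- Week 6: 42 days; 42 − 7 = 35 to 42 + 7 = 49.
- Week 12: 84 days; 84 − 7 = 77 to 84 + 7 = 91.

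**Examples at nominal dates**

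| Course | Plan (days) | From Sun-Start (days) | Shortfall |
|---|---|---|---|
| SD week 6, PD week 12 | 84 − 42 + 1 = 43 | 84 + 1 = 85 | 42/85 = 49% |
| SD weeks 6 and 12, PD week 24 | 168 − 42 + 1 = 127 | 168 + 1 = 169 | 42/169 = 25% |
| Same, week 6 not scanned | 168 − 84 + 1 = 85 | 169 | 84/169 = 50% |
| SD from week 6, PD week 48 | 336 − 42 + 1 = 295 | 336 + 1 = 337 | 42/337 = 12.5% |
| Clinical benefit, SD week 6, no later scan or event | 42 − 42 + 1 = 1 | 42 + 1 = 43 | 42 days |

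Rows 2 and 3 are the same disease course. Attendance at one scan moves the reported value from 127 to 85 days.

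**Average effect, under assumptions that are not in the documents.** A simulation took exponential time to progression with a median of 6, 9 or 12 months, and 0, 10 or 20% of week-6 scans missed. The mean shortfall was 42 days with none missed, about 46 days with 10% and 49 to 50 days with 20%.

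**Responders.** Clinical benefit also starts late for them, at their first scan without progression. If that scan already shows CR or PR, duration of response and duration of clinical benefit share start, end and handling of event-free patients, and so are identical.

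**The case against.** The strongest reply is that the rule is explicit and reproducible, that protocol and SAP agree on the start for stable disease, and that both arms are treated alike. On that view the durations are correct for what they are defined to be: time from first documented SD. The section heading is weak evidence of another intended origin, because it also covers duration of response, which properly starts at first CR or PR. The same holds for the objective, "To evaluate response and its duration according to RECIST 1.1 criteria from Sunitinib Start Visit", which does not name SD. This part stands: the SAP does not depart from the protocol, and the heading alone does not make the rule a contradiction. The point rests on how SD is judged at the first scan and on the dependence on attendance, and agreement between the two documents removes neither.

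It is also fair that neither duration is among the secondary endpoints in Protocol section 10.1 or SAP section 3.2, that neither is tested, and that PFS, TTP and a swimmer plot already run from sunitinib start. That limits the importance of the point.

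Three stronger readings are tempting, and the documents support none of them.

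- *The rule biases the comparison between arms.* Both arms have the same schedule after Sun-Start, so with full attendance the shift is about equal. Bias would need missed or unevaluable early scans to differ by arm, and nothing in the documents shows that.
- *The distortion falls where the arms are most likely to differ.* The proportional shortfall is largest when control is short, but nothing in the documents says that the arms differ most there.
- *A common origin would make SD duration equal PFS.* It would not. SD duration counts only deaths due to progression, whereas PFS counts death from any cause before the end of the trial.

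**Conclusion.** The point holds as a minor measurement flaw in two descriptive summaries. For patients on the schedule of version 4.0 or later, duration of stable disease and duration of clinical benefit fall short of time from Sun-Start by 35 to 49 days when week 6 is the first scan scored, and by 77 to 91 days when week 12 is. Patients with the same course can therefore receive different values. OS, PFS, TTP, ORR, DCR and duration of response are unaffected.

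The figures assume scheduled scans within their windows and sunitinib started on the Sun-Start date. The Sun-Start CT may fall on another day (Protocol section 7.2.1.5), so the offset from the CT itself can differ. For intermediate-risk patients enrolled before version 4.0 no offset can be computed, because the current documents do not give their scan schedule.

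**What to change.** In Protocol section 10.2.2.2 e) and SAP section 6.3.6, start duration of stable disease and duration of clinical benefit at the same baseline date as PFS. Keep first CR or PR as the start for duration of response.

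The baseline for intermediate-risk patients enrolled before version 4.0 has to be reconciled first. Protocol sections 10.2.2.1 and 10.2.2.2 use the first imaging after nephrectomy. SAP section 6.3.6 uses the date of the visit after the nephrectomy visit for patients who started sunitinib late or never. One of these should be stated and used throughout.

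A related gap can be closed in the same edit: the SAP says how event-free patients are counted for response and clinical benefit, but gives no such rule for stable disease.

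The cost is a sentence or two in each document and a changed origin variable, with no new data. With full attendance the figures lengthen by about 6 weeks in both arms. The small downside is more overlap with PFS among patients whose best response is SD. A table footnote should say that SD duration still counts only deaths due to progression.
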